9.8.3. Stopping Rules

Safety data review including AEs and laboratory assessments will be performed on an ongoing basis. The stopping rules discussed in this section will apply only to the dose titration period of the study. If dosing of an individual patient is suspended during the open-label period, the Investigator will consult with the Medical Monitor to determine whether the patient may resume treatment or whether he needs to be excluded from further dosing.

During the study, sites are required to report all AEs as defined in Section 9.8.2 and Section 10.4. If safety concerns arise at any time, dosing may be stopped until these concerns have been addressed. Dosing will be interrupted to allow for review of cumulative safety data by the DSMB if any of the following conditions are met:

- >2 severe AEs or ≥ 3 moderate AEs considered to be possibly/probably or definitely related to investigational drug product
- Any SAE considered to be possibly/probably or definitely related to investigational drug product
- ≥ 2 patients develop 2 consecutive serum creatinine levels $\geq 2X$ their respective average pre-treatment values
- ≥ 2 patients develop 2 consecutive instances of unexplained protein in urine $>2+$

- Any unexplained gamma glutamyl transferase (GGT) >3X upper limit of normal (ULN) in combination with bilirubin >2X ULN
- 2 consecutive instances of unexplained activated partial thromboplastin time (aPTT) >45 seconds in the same patient

During the dose titration period of the study, the DSMB will be notified by the Sponsor within 24 hours of the Sponsor learning of any of the events listed above. Dosing may also be interrupted or halted if warranted at the discretion of the Sponsor or Investigator. Any decisions related to dose adjustment, delay, or stopping during dose titration will be communicated by the Sponsor to all sites immediately. In addition, Investigators may, in the event of an emergency, directly contact their peers at other sites to communicate safety concerns.

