9.8.2. Safety Monitoring During Dose Titration

Safety data review including AEs and laboratory assessments will be performed on an ongoing basis. The following procedures will be implemented to minimize the risk to study patients during dose titration.

- All serious adverse events (SAEs), regardless of relatedness, will be reported by the Investigators to the Sponsor immediately and no more than within 24 hours of occurrence.
- All AEs classified as possibly/probably or definitely related to investigational drug product, regardless of severity, will be reported by the Investigators to the Sponsor immediately, within 48 hours of occurrence.
- The Medical Monitor will review safety data including clinical and laboratory information on an ongoing basis. Summary reports of these reviews will be distributed as warranted to all participating Investigators, specifically when treatment-related AEs have been reported.
- Prior to dose administration, the Investigator will review all AEs and all laboratory values for the specific patient and will proceed with dosing only if he or she deems that it is safe to do so based on all available information.

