9.8.4. Data Safety Monitoring Board

An independent DSMB will be employed to review all available safety data for all patients at the time point when the last patient has completed 2 infusions at 30 mg/kg (approximately Week 8). This aggregate data review will be blinded unless the DSMB specifically requests unblinding at the patient or group level based on safety data summaries. The DSMB will be charged with advising the Sponsor about whether transitioning into the open-label extension period of the protocol is appropriate based on aggregate safety data from the double-blind dose-titration period. Based on the results of the DSMB review, the Sponsor will determine whether to roll over patients into the open-label extension period.

Any decision to interrupt, restart, or discontinue the study will be made by the Sponsor in consultation with the DSMB.

A formal DSMB meeting may be convened at any time if requested by the Sponsor of this study. The DSMB charter will provide further detail on the meeting and decision-making process involving the DSMB.

The outcome of any DSMB meeting will be communicated to the Investigators by the Sponsor. The relevant regulatory authorities will be promptly notified of study suspension or discontinuation related to safety concerns. Any suspension or discontinuation of the trial for any reason will also be promptly reported to the relevant Institutional Review Boards (IRB)/Independent Ethics Committee (IEC).

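### Mandatory pause criteria and the 24-hour DSMB notice end with titration, so in the visible text the 4 ex-placebo patients' first casimersen exposure has no mandatory trial-level trigger

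*Protocol*

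**What the plan says.** **Scope of the rules.** Protocol 9.8.3 lists six criteria under which dosing must be interrupted for DSMB review:
- counts of related severe or moderate AEs;
- any related SAE;
- two consecutive raised creatinine values in at least 2 patients;
- two consecutive urine-protein findings in at least 2 patients;
- raised GGT together with raised bilirubin in any patient;
- two consecutive unexplained aPTT values above 45 seconds in one patient.

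The section limits them: "The stopping rules discussed in this section will apply only to the dose titration period of the study". The notice is limited in the same way: "During the dose titration period of the study, the DSMB will be notified by the Sponsor within 24 hours".

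**Open-label route.** The same section gives a patient-level path: "If dosing of an individual patient is suspended during the open-label period, the Investigator will consult with the Medical Monitor". It also allows, without requiring, dosing to be stopped whenever a safety concern arises.

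**Reporting.** Section 9.8.3 says "During the study, sites are required to report all AEs as defined in Section 9.8.2 and Section 10.4", which suggests that the 9.8.2 reporting rules continue. Section 9.8.2, however, is headed for titration and opens "The following procedures will be implemented to minimize the risk to study patients during dose titration".

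**DSMB.** Under 9.8.4 the board will "review all available safety data for all patients at the time point when the last patient has completed 2 infusions at 30 mg/kg", before rollover. It adds "Any decision to interrupt, restart, or discontinue the study will be made by the Sponsor in consultation with the DSMB" and "The DSMB charter will provide further detail on the meeting and decision-making process involving the DSMB". The Sponsor may call a DSMB meeting at any time. SAP 4.5.1 describes DSMB-monitored safety reviews about every 6 to 12 months.

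**Open-label dosing and data.** Table 2 footnote i puts every patient on 30 mg/kg or the highest tolerated dose; 9.6 states 30 mg/kg. Section 9.7 makes no provision for altering the dose. Table 3 schedules laboratories at each of Open Label Weeks 1 to 8, plus ECGs and examinations. SAP 4.3.2 keeps the original assignment blinded until final database lock.

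**The concern.** In a first-in-human study, the patient's first weeks on drug are when a pre-agreed trigger is most useful. For 8 patients those weeks fall inside titration, where the criteria apply. For the other 4 they fall just after the criteria end.

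During titration, one drug-related SAE, or two consecutive unexplained aPTT values above 45 seconds in one patient, obliges a pause and a DSMB review. In Open Label Weeks 1 to 8 the visible text leaves the same finding to reporting, consultation and discretion. SAE reporting would not by itself carry a non-serious laboratory signal to the DSMB.

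Table 3 shows that the authors saw the start of open-label treatment as a period needing closer monitoring. It brings back weekly laboratories, but no trial-level action is tied to them. Section 9.8.1 names renal events as the most likely drug-related AEs, and the creatinine and urine-protein criteria need two consecutive values. Weekly sampling suits them.

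**Working it through.** **1. The plan's own figures.** Protocol 7.1 randomises 12 patients 2:1: 12 × 2/3 = 8 and 12 × 1/3 = 4, as stated. Protocol 9.9.2 ends blinded dosing about 4 weeks after the last enrolled patient has had 12 weeks. With treatment to Week 144, that patient's open-label time is 144 − (12 + 4) = 128 weeks, matching 8.3.

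**2. Who starts outside the rules.** The placebo patients: 4/12 = 33%.

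**3. Starting dose.** The active arm began at 4 mg/kg (7.1). The ratio for an ex-placebo patient depends on the open-label dose:
- 30 mg/kg: 30/4 = 7.5
- 20 mg/kg: 20/4 = 5
- 10 mg/kg: 10/4 = 2.5

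Because all 8 active patients start at 4 mg/kg by design, 0 of 8 in the pre-rollover data had a first dose of 30 mg/kg.

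**4. What Table 3 supplies.** There are 8 weekly laboratory visits per patient. Section 10.3.3 puts laboratories before dosing, so the Open Label Week 1 sample precedes the first open-label infusion. That leaves 8 − 1 = 7 values after it and 7 − 1 = 6 consecutive weekly pairs. Later scheduled laboratories are 4 weeks apart up to study Week 36 and 12 weeks apart after that (7.1). Open Label Week 1 falls at a different study week for each patient, so early enrollees may go straight to 12-week spacing.

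**5. Would the existing criteria fire in 4 patients?** The documents give no event rates. Let p be an assumed probability that a patient meets a criterion in the window, independent between patients. Then

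P(at least 1 of n) = 1 − (1 − p)^n

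P(at least 2 of n) = 1 − (1 − p)^n − n·p·(1 − p)^(n−1)

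For n = 4 and p = 0.10: 1 − 0.6561 = 0.344, and 1 − 0.6561 − 0.2916 = 0.052.

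| Assumed p | At least 1 of 4 | At least 2 of 4 | At least 2 of 12, same p |
|---|---|---|---|
| 0.05 | 0.185 | 0.014 | 0.118 |
| 0.10 | 0.344 | 0.052 | 0.341 |
| 0.20 | 0.590 | 0.181 | 0.725 |
| 0.30 | 0.760 | 0.348 | 0.915 |

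Carried over unchanged, the two-patient creatinine and urine-protein rules would seldom respond to the newly exposed group alone. The last column applies only if the 8 patients already on drug share the same p.

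**6. Is any remaining safeguard a mandatory trigger in this window?**
- Stopping for a safety concern (9.8.3): permitted, not required.
- DSMB consultation (9.8.4): required once a decision to interrupt is being made, but nothing obliges that decision. Meetings outside the planned review are at the Sponsor's request.
- SAE reporting (11.5), SUSAR reporting (11.3.8) and IRB/IEC notice (14.2): these move information but set no dosing action.
- Laboratory review before the first open-label dose (Table 3 footnote c, 10.3.3): required, for that dose only.
- Periodic DSMB review (SAP 4.5.1): follows the calendar, not events.

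None is a mandatory trial-level trigger.

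**The case against.** The strongest reply is that the transition was planned. The DSMB reviews cumulative data before rollover. By then each active patient should have had at least 2 infusions at 30 mg/kg, and the last enrolled patient about 10 before rollover (Weeks 7 to 16: 16 − 7 + 1). Laboratories are reviewed before the first open-label dose, and Table 3 adds a dedicated schedule. Acute reactions are covered by trained staff, resuscitation equipment, at least 1 hour of observation (9.8.1) and vital signs at 5, 30 and 60 minutes (10.3.1). Whether the next control should be a rule or Sponsor judgement with DSMB advice is a legitimate choice. All of this stands, and it is why the point is an improvement and not an error. It does not replace a trigger for delayed laboratory findings in patients who were never titrated.

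A second objection is to an automatic pause of all 12 patients. Once everyone is known to be on drug, a relatedness category that includes events that merely could be related would make such a pause easy to set off, and it would interrupt 8 patients already on 30 mg/kg. This also stands. The fix therefore extends notice and leaves wider pauses to judgement.

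A third is that the visible text is incomplete. Parts of 7.2, 7.4, section 9 (including the ends of 9.6 and 9.8.1) and 10.4 are redacted, and the DSMB charter is not available. A trigger or a step-up could sit there. This limits the claim to what can be read.

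A reader might go further and infer that these patients are unmonitored, that the protocol contradicts itself, or that a 7.5-fold starting dose means 7.5-fold risk. The documents support none of these: oversight continues, the scope limit is explicit, and the ratio compares doses only. Nor does the 6-to-12-month cycle give a number of infusions before the next DSMB review, because SAP 4.5.1 gives no starting point for it.

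**Conclusion.** The point holds as a cheap improvement to a stated design choice. In the visible text, 4 of 12 patients begin casimersen after the mandatory pause criteria and the 24-hour DSMB notice have ended. They start at up to 7.5 times the active arm's first dose, and no mandatory trial-level trigger is tied to weekly laboratories that are already collected.

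The scope of the rules, the allocation and the Table 3 schedule are read directly from the documents. The absence of a step-up or an open-label trigger is a statement about unredacted text only. The 5% figure for a two-patient rule in 4 patients assumes a 10% rate and independence; across assumed rates of 5% to 30% it runs from about 1% to 35%. No estimate of harm prevented can be made from these documents, and none is claimed.

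SAP 4.5.1 describes periodic reviews in the past tense, so the window may already have closed for these patients. The point concerns the protocol as written. Confidence is medium, mainly because of the redactions and the unseen charter.

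**What to change.** Amend Protocol 9.8.3 as follows, for each patient's own Open Label Weeks 1 to 8:

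- Apply the 24-hour Sponsor-to-DSMB notice for every listed criterion to all 12 patients. Covering everyone avoids revealing the original assignment.
- Restart the AE counts at Open Label Week 1.
- Keep each patient's average before the first study infusion as the creatinine reference, so that the same rule serves both original arms.
- Also notify the DSMB when a single patient meets the creatinine or the urine-protein criterion.
- If a patient meets the GGT-with-bilirubin or the two-consecutive-aPTT criterion, hold dosing in that patient until the DSMB advises.
- Leave any other pause to the Sponsor in consultation with the DSMB, as 9.8.4 already provides.
- State that the 9.8.2 reporting rules and pre-dose review apply in this window.

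Add to 9.8.4 one DSMB review of the Table 3 data after the last patient completes Open Label Week 8. If the DSMB charter already provides any of this, a cross-reference is enough.

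The cost is protocol and charter wording, one more DSMB data transfer, some extra notices and a possible temporary hold in an affected patient. No new visit or sample is needed.

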11.3.4. Severity of Adverse Events

Note that severity is not the same as "seriousness", which is defined in Section 11.2.2 and which serves as a guide for defining regulatory reporting obligations.

The Investigator will assess the severity of all AEs as Mild, Moderate, or Severe, based on the following definitions.

Mild: The event does not interfere with the patient's usual activities.

Moderate: The event interferes with the patient's usual activities.

Severe: The event prevents the patient from undertaking their usual activities and requires therapeutic intervention or cessation of the investigational drug product.

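### The first dose-titration stopping criterion counts severe and moderate related AEs separately: three moderate events force DSMB review, but one severe plus two moderate do not if none is serious or meets a laboratory criterion

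*Protocol*

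**What the plan says.** Protocol 9.8.3 makes the listed conditions mandatory triggers during dose titration: "Dosing will be interrupted to allow for review of cumulative safety data by the DSMB if any of the following conditions are met". The first condition has two limbs joined by an *or*. The severe limb reads ">2 severe AEs or", and the second limb is at least 3 "moderate AEs considered to be possibly/probably or definitely related to investigational drug product". The next condition is a trigger on a single event: "Any SAE considered to be possibly/probably or definitely related to investigational drug product". The remaining conditions are laboratory ones (creatinine, urine protein, GGT with bilirubin, aPTT). Outside the list, a halt is optional: "Dosing may also be interrupted or halted if warranted at the discretion of the Sponsor or Investigator".

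Section 11.3.4 gives each event one grade: "The Investigator will assess the severity of all AEs as Mild, Moderate, or Severe". Moderate means interference with usual activities. Severe is defined as follows: "The event prevents the patient from undertaking their usual activities and requires therapeutic intervention or cessation of the investigational drug product". The same section opens "Note that severity is not the same as" seriousness, which is defined separately in 11.2.2.

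Neither document states a count that combines the two grades. SAP 4.1 only mentions that predefined stopping criteria exist. The DSMB charter, to which Protocol 9.8.4 refers for further detail, is not among the documents.

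**The concern.** A safety trigger should never become less responsive when an event is worse. Because the limbs are counted apart, a severe event adds nothing towards the moderate limb, and a moderate event adds nothing towards the severe limb. A mix of the two grades can then be worse than three moderate events and still not reach either limit.

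This is one of the mandatory triggers in a first-in-human titration. Patients move up a dose level every 2 weeks (Protocol Table 2, dosing footnote), so a later trigger can mean further infusions or a higher dose before the DSMB looks. If no further related event follows a silent mix, this condition never fires. The Sponsor's duty in 9.8.3 to notify the DSMB within 24 hours covers only the listed events, so a silent mix does not create that duty either. The first scheduled DSMB review comes once the last patient has had two infusions at 30 mg/kg (9.8.4).

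**Working it through.** There is no sample size or power figure to reproduce; Protocol 12.2 says that no formal calculation was made. The check is a complete enumeration of the rule and needs no assumed AE rate.

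**Inputs.** Let *s* and *m* be the numbers of related severe and related moderate AEs. All are taken as non-serious and as meeting no laboratory criterion, since otherwise another condition fires. The limits come from Protocol 9.8.3 and the single grade per event from 11.3.4. The protocol does not say whether this condition counts events within a patient or across the study; the arithmetic is the same either way.

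**Rules compared.**
- Printed: *s* > 2 or *m* ≥ 3. For whole numbers, *s* > 2 is the same as *s* ≥ 3.
- Alternative: *s* ≥ 2 or *m* ≥ 3. Writing >2 beside ≥3 for the same limit is odd, and a drafting slip or a PDF-reading error is possible.
- Pooled: *s* + *m* ≥ 3.
- Pooled plus severe limb: *s* + *m* ≥ 3 or *s* ≥ 2.

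| (*s*, *m*) | Printed | Alternative | Pooled | Pooled + severe limb |
|---|---|---|---|---|
| (0,3) | fires | fires | fires | fires |
| (1,2) | silent | silent | fires | fires |
| (2,0) | silent | fires | silent | fires |
| (2,1) | silent | fires | fires | fires |
| (2,2) | silent | fires | fires | fires |
| (1,3) | fires | fires | fires | fires |
| (3,0) | fires | fires | fires | fires |

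**Step 1: silent mixes of three or more events.** The printed rule is silent when *s* ≤ 2 and *m* ≤ 2. With *s* + *m* ≥ 3 that leaves (1,2), (2,1) and (2,2). The alternative is silent when *s* ≤ 1 and *m* ≤ 2, which leaves only (1,2). Both pooled rules leave none.

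**Step 2: regrading one moderate event as severe.** As printed, (0,3) → (1,2) and (1,3) → (2,2) switch a triggered rule off. Under the alternative, (0,3) → (1,2) still does. Under either pooled rule no such swap exists, because *s* + *m* is unchanged and *s* only rises.

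**Step 3: latest possible trigger.** This is the largest silent total plus one.
- Printed: (2 + 2) + 1 = 5th event.
- Alternative: (1 + 2) + 1 = 4th event.
- Pooled, with or without the severe limb: 2 + 1 = 3rd event.

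Against the pooled count the delay is at most 5 − 3 = 2 events as printed, and 4 − 3 = 1 event under the alternative.

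**Step 4: what a delay means in dosing.** With 12 patients dosed weekly, each week of delay is up to 12 infusions, 8 of them active. Dose steps fall at Weeks 3, 5 and 7, so only patients still in Weeks 1 to 6 can reach a higher dose in the meantime. The documents give no AE rate, so the delay cannot be turned into weeks.

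**The case against.** **The SAE condition covers much of this.** Severe and serious lie close together. A severe event needs intervention or cessation of drug, and 11.2.2 lets an important medical event be called serious on medical judgment. Some severe related events will therefore trigger review on their own. This stands, and it narrows the case. It does not remove it: 11.3.4 separates severity from seriousness, and the severe limb would be redundant if every severe related event were also serious.

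**Other safeguards exist.** Related AEs of any severity must reach the Sponsor within 48 hours, the Medical Monitor reviews data on an ongoing basis, and the Investigator reviews the individual patient before each dose (9.8.2). The Sponsor may halt dosing (9.8.3) or convene the DSMB (9.8.4) at any time, and the DSMB may ask for unblinded safety data at any time (9.9.3). A reader might infer from the gap that patients go without oversight until the scheduled review at about Week 8. The documents do not support that. What remains is that no count in these provisions compels a halt, so after a silent mix the halt is discretionary.

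**The benchmark and the symbol are open.** A reader might take the 2-event delay as a plain fact about the rule. It holds only for the printed >2, and only against a pooled count of 3 that the protocol does not state. If moderate was meant as moderate or worse, there is no gap at all, but 11.3.4 defines the grades separately and 9.8.3 does not say so. The DSMB charter might also deal with mixed grades. These points limit the size of the finding. They do not touch the (0,3) → (1,2) reversal, which occurs under both severe limits.

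**Reach is limited.** The rule applies to titration only. SAP 4.5.1 describes periodic safety reviews in the past tense, so titration was probably over when the SAP was written (an inference).

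**Conclusion.** The concern holds in a limited form. On the wording of 9.8.3, three moderate related AEs force interruption and DSMB review, while one severe plus two moderate do not, under a severe limit of either more than 2 or at least 2. As printed, (2,1) and (2,2) are silent too, with a delay of up to 2 events against a pooled count. With a limit of at least 2, only (1,2) is silent and the delay is at most 1 event.

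This rests on three assumptions: every event in the mix, moderate ones included, is non-serious; none meets a laboratory criterion; and moderate does not mean moderate or worse. How often such a mix would arise cannot be judged from the documents.

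The gap concerns one mandatory trigger in dose titration. It should be fixed because the rule gives the wrong ordering as written and the correction is short. A reader might infer that it weakens the study's safety results. It does not: no endpoint or SAP analysis depends on the rule.

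**What to change.** Reword the first condition in 9.8.3 to *≥3 related AEs of moderate or greater severity*. If a limit of at least 2 severe events was intended, keep *or ≥2 related severe AEs* as a separate limb. Pooling alone would delay that trigger from the 2nd event to the 3rd, or lose it if titration ends on (2,0). The sponsor and DSMB should confirm the severe number, and the charter should carry the same text. If titration is already complete, check its related-AE counts for the three silent mixes and do not carry the wording into later protocols.

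The cost is a one-sentence amendment and matching charter text, with these operational effects:
- **Against the printed rule, pooling alone:** added interruptions only for titrations that would end on (1,2), (2,1) or (2,2). Some other interruptions come 1 or 2 events earlier.
- **Against the printed rule, pooling plus the severe limb:** (2,0) is also added, and an interruption can come up to 3 events earlier. For example, for two severe, then two moderate, then any fifth event, the new rule fires at the 2nd event and the printed rule at the 5th (5 − 2 = 3).
- **Against a limit of at least 2 severe, pooling plus the severe limb:** only (1,2) is added, and no interruption comes more than 1 event earlier (4th to 3rd).
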